The intervention will be considered feasible and acceptable if participants attend more than 70% (i.e., >4) of sessions. Differences in feasibility also will be compared according to demographic variables and use history variables. Acceptability will be assessed by completion of self-monitoring forms, attendance during pregnancy, and the Acceptability of Intervention (AIM) measure. Retention also will be documented and will be defined as the proportion who provide data at 12-16 weeks postpartum relative to the total number enrolled. We will present these measures of feasibility and acceptability to the collaborative to solicit their input and may add other measures of feasibility and acceptability based on their recommendations.

2. * Describe the relevant prior experience and gaps in current knowledge including preliminary data. Provide for the scientific or scholarly background for, rationale for, and significance of the research based on existing literature and how it will add to existing knowledge:

B. SIGNIFICANCE

B1. People from marginalized communities are more likely to use tobacco during pregnancy (Agrawal et al., 2019) and are under-represented in tobacco treatment research (Weinberger et al., 2022). Rates of prenatal tobacco use have not decreased among Black people (Agrawal et al., 2019; Li et al., 2018) and are higher for sexual minority people (Beck et al., 2021; Gonzalez et al., 2019). At least 40% of individuals who quit smoking during pregnancy will resume smoking in the postpartum (Fingerhut et al., 1990; Rockhill et al., 2016), most of them within 100 days of delivery ([name] et al., 2022). Younger, less educated, Black people are more likely to relapse to smoking postpartum (Orton et al., 2018; Rockhill et al., 2016) and, on average, Black people smoke for more years prior to quitting (Jones

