Relatedly, we examined the effectiveness of two postpartum smoking relapse preventions as a function of prenatal depressive symptoms ([name] et al., 2020). People with clinically significant depressive symptoms late in pregnancy did not maintain smoking abstinence in the postpartum if they received a standard intervention with behavioral techniques to manage cigarette cravings (SUPPORT). However, as seen in Figure 3, those who were depressed late in pregnancy were more successful maintaining abstinence if they received a smoking abstinence intervention that was tailored to psychosocial factors such as mood (STARTS). These results highlight the importance of depressive symptomatology in postpartum tobacco abstinence and the significance of addressing prenatal depressive symptoms for long-term impact on maternal and child health. Thus, we propose to

invite people who use tobacco and cannabis and experienced elevated depressive symptoms during pregnancy to partner with us in an intervention development project to reduce tobacco-related health inequities.

Study Design

1. Total number of subjects to be enrolled at this site (enter -1 for chart reviews, banking, registries):

25

2. Describe and explain the study design:

This study is an experimental, single-arm feasibility trial.

3. Describe the primary and secondary study endpoints:

The primary outcomes of the trial is the feasibility and acceptability of the novel intervention and abstinence from tobacco and cannabis use. Feasibility and acceptability of the intervention will be assessed using attendance, completion of intervention-related procedures, and the Acceptability of Intervention Measure (AIM). Abstinence will be measured by proportion of the participants who self-report no use of either substance and by calculating the proportion of participants with negative urine screens for THC and COT. Secondary outcomes include changes in depressive symptoms, tobacco, and cannabis use from the baseline assessment in pregnancy to 3 months postpartum.

4. Provide a description of the following study timelines:

Duration of an individual subject's active participation:

Depending on gestation age at enrollment, subjects will actively participate in the study for approximately 6 to 12 months.

Duration anticipated to enroll all subjects:

9/30/2026

Estimated date for the investigator to complete this study (complete primary analyses):

10/1/2027

5. List the inclusion criteria:

- (1) <26 weeks of gestation

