- (2) English speaking
- (3) confirmed pregnant
- (4) plan to remain pregnant
- (5) use of combustible tobacco at least once a week during pregnancy, or at least once a week in the 3 months before pregnancy if stopped
- (6) use of cannabis at any frequency during pregnancy or in the 3 months before pregnancy if stopped

English speaking is a requirement since study materials are in English and intervention sessions will be conducted in English.

6. List the exclusion criteria:

- (1) current opioid use or active treatment for Opioid Use Disorder
- (2) unable to provide informed consent in English
- (3) under 18 years old

7. Will children or any gender, racial or ethnic subgroups be explicitly excluded from participation?

☒ Yes ☐ No

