*** Identify the subgroups and provide a justification:**

We exclude individuals under age 18 from this work because the perinatal concerns and treatments for depression of individuals younger than age 18 are likely to differ from those of individuals 18 years of age or older and would require developmentally appropriate assessments and interventions.

8. Describe the power analysis used and cite your method of statistical analysis. If a power analysis is not possible, thoroughly justify the sample size required for the study, including appropriate literature citation (alternatively provide page reference in attached protocol):

Chi-square tests will be used to calculate differences in feasibility as a function of key intersecting identities (e.g., age, race, ethnicity, SM status) and use history variables. If feasibility is found to be significantly different by race or SM status, the analyses will be weighted to account for differences in attrition. We will assess the preliminary efficacy of the novel intervention to promote self-reported abstinence from tobacco and cannabis at the end of pregnancy (Time 3) and 12-16 weeks postpartum (Time 4). The proportion of self-reported abstinence among participants in the INT and EUC groups at Times 3 and 4 will be compared using chi-square tests of difference. We will stratify by race and sexual orientation to test for intersectional effects. Secondary analysis will examine differences in biochemically verified abstinence (urine dip test for presence of cotinine or THC) and depressive symptoms between INT and EUC using chi square tests and compare depressive symptoms (EPDS) scores in the two groups using two-sample t-tests. The Cochran Q test will be applied to self-reported tobacco and cannabis use across the 4 time points within the INT group to test whether there has been a change in the ratings over time. Next, a generalized linear mixed effects model (GLMM) with a logit link will be used to test the treatment effect (INT vs. EUC) and treatment by time interaction to test whether the rate of abstinence over time was steeper among the INT group compared to the EUC group. We have 70% power to detect a 15% difference in quit rates between INT and EUC, assuming a 25% intervention arm quit rate and 10% control arm quit rate.

Pregnant Women

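### Cochran's Q, the only planned test of tobacco and cannabis use that one arm can support, ignores direction and does not test the stated change from baseline to 3 months postpartum

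*Protocol*

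**What the plan says.** Study Design, item 2 states: "This study is an experimental, single-arm feasibility trial". Item 1 sets enrolment at 25. Item 3, like Study Aims, item 1, makes abstinence from tobacco and cannabis a primary outcome. It makes change in tobacco use, cannabis use and depressive symptoms, from the baseline assessment to 3 months postpartum, secondary.

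The analysis text in item 8 compares two groups: "The proportion of self-reported abstinence among participants in the INT and EUC groups at Times 3 and 4 will be compared using chi-square tests". The tests of verified abstinence and of depressive symptoms, and the logistic mixed model, are also INT versus EUC. Two planned analyses need no control group:

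- feasibility by subgroup: "Chi-square tests will be used to calculate differences in feasibility as a function of key intersecting identities";
- substance use over time: "The Cochran Q test will be applied to self-reported tobacco and cannabis use across the 4 time points within the INT group", with the purpose "to test whether there has been a change in the ratings over time".

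No direction or pairwise contrast is attached to the second.

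The inclusion criteria (item 5) require recent use of both substances but admit people who have stopped. For cannabis the wording is "use of cannabis at any frequency during pregnancy or in the 3 months before pregnancy if stopped"; the tobacco criterion has the same structure with weekly use. The background (Study Aims, item 2, B1) says: "At least 40% of individuals who quit smoking during pregnancy will resume smoking in the postpartum".

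**The concern.** Once the comparisons with the absent EUC group fall away, Cochran's Q is the only p-value the plan gives for tobacco or cannabis use. It answers whether the proportion using is the same at all four visits. The trial needs to know whether fewer people use at 3 months postpartum than at baseline, and whether quitting in pregnancy lasts.

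These questions can have opposite answers. The four visits span delivery, and the protocol itself expects substantial postpartum relapse. A significant Q could come from quitting, from relapse, or from a dip that has fully reversed by T4. In a section that speaks of preliminary efficacy, such a result is easily taken as support for the intervention.

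The baseline visit adds to this. Participants enter because of recent use, so with no control group a fall from T1 mixes any intervention effect with selection and spontaneous quitting.

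**Working it through.** **The plan's own figure.** None is given for Q. The one power figure in item 8 (70% for 25% versus 10%) concerns INT versus EUC. At an assumed two-sided 5% level it needs 79 per arm, so it says nothing about this test in 25 people.

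**Which tests can be run in one arm.** The INT versus EUC chi-square tests, the t-tests and the treatment and treatment-by-time terms of the mixed model all need EUC. The chi-square tests of feasibility by subgroup can be run but do not concern substance use. Cochran's Q remains.

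**Direction.** With k = 4 visits, C_j users at visit j, R_i visits with use for person i, and N total uses,

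Q = (k − 1)[k ΣC_j² − N²] / [kN − ΣR_i²], referred to chi-square with 3 df.

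Take 25 people with nested patterns (those using at a visit with fewer users also use at every visit with more).

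- *Cessation, 20/14/12/10.* N = 56; ΣC_j² = 400 + 196 + 144 + 100 = 840; ΣR_i² = 10×16 + 2×9 + 2×4 + 6×1 = 192. Q = 3(3360 − 3136)/(224 − 192) = 672/32 = 21.0.
- *Worsening, 10/12/14/20.* The same sums in reverse order: Q = 21.0.
- *Dip and full return, 15/8/15/15.* N = 53; ΣC_j² = 739; ΣR_i² = 8×16 + 7×9 = 191. Q = 3(2956 − 2809)/(212 − 191) = 441/21 = 21.0.

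All three give p = 0.0001. The T1-to-T4 change in the number using is −10, +10 and 0. An exact McNemar test of T1 against T4 separates them: 10 discordant pairs, all towards abstinence (p = 2 × 0.5¹⁰ = 0.002); 10, all towards use (same p, opposite sign); and none (p = 1).

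**How often Q rejects.** Simulation at the 5% level, with assumed use at T1/T2/T3/T4 and latent within-person correlation 0.5:

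| Profile | n = 25 |
|---|---|
| Sustained cessation, 80/40/40/40% | 96% |
| Full relapse by T4, 80/40/60/80% | 96% |
| Worsening, 40/40/60/80% | 95% |

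Repeat runs with other random seeds differ by about one point.

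A second set uses transition rates, with relapse placed near the protocol's 40%; all rates are assumptions. If half use at T1, nobody quits, and non-users relapse at 25% and then 20% (cumulative 1 − 0.75 × 0.80 = 40%), Q rejects in 81% of runs with no cessation at all. If 70% use at T1, 25% of them quit in pregnancy, and relapse is 30% then 20% (1 − 0.70 × 0.80 = 44%), Q rejects in 63% of runs. In 46% of all runs it rejects while use at T4 is at or above T1.

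**The baseline visit.** Suppose each person's propensity to use never changes (beta, concentration 4, mean 0.8 / 0.7 / 0.6 before selection; n = 25). The rejection rate then depends on how far selection fixes T1 status:

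| Share forced to be users at T1 | Rejection rate |
|---|---|
| All (worst case) | 38 / 77 / 97% |
| 75% | about 18 / 37 / 59% |
| None (T1 is simply use at that visit) | about 4% |

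The protocol text gives neither the expected share using at T1 nor the recall window of the T1 questionnaires, so the position on this scale is unknown.

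**The case against.** The protocol does not say that Q shows cessation. It says Q tests for change, which it does, and a high rejection rate when use really changes is the test working. Abstinence is also to be reported as proportions, so a reader could see relapse beside the p-value. T1 belongs in the analysis because the secondary outcome is defined from baseline. The bigger defect in item 8 is the two-arm plan itself, and correcting that will force a rewrite of the paragraph anyway.

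Much of this stands. The fault is not a false statement about Q; it is that no directional within-group analysis of substance use is planned. Proportions beside Q would help, but the only inference would still be one that does not address the stated outcome. Deleting EUC from the text would leave Q as the sole test, so it needs its own correction.

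Four stronger readings are tempting, and the document does not support them:

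- *Q is the only planned test that suits one arm.* The feasibility chi-square tests suit it too. Q is the only one for substance use.
- *Eligibility makes everyone a user at T1.* Criteria 5 and 6 admit people who have stopped. The 38/77/97% figures are an upper case, and the effect may be negligible.
- *The plan discards anyone who misses a visit.* The standard test needs complete rows, but the protocol does not state how missing visits are handled, and an SAP may do so.
- *T1 should be left out.* That would abandon the change from baseline which the protocol defines as an outcome.

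**Conclusion.** The point holds in this form: the one runnable test of tobacco and cannabis use is blind to direction, does not test change from T1 to T4, and cannot by its p-value support a claim of cessation. The identical Q of 21.0 for three opposite courses is exact arithmetic on constructed data. The rejection rates of 95% to 96% rest on assumed profiles and a latent correlation of 0.5; the 81% and 63% rest on assumed transition rates, with only relapse tied loosely to the protocol.

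The baseline concern is real but of unknown size: from nominal (about 4%) to 38/77/97% if everyone uses at T1. It is a reason to show the two T1 groups separately and to call the change uncontrolled, not proof that Q is inflated in this trial.

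It deserves correction because abstinence is a primary outcome. It does not touch the feasibility and acceptability aims.

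**What to change.** In Study Design, item 8, replace Cochran's Q as the test of substance use, taking T1 to T4 as defined under Research Activities:

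- For each substance, report the proportion abstinent at T2, T3 and T4 with exact 95% intervals, separately for participants using at T1 and those already stopped at T1.
- Pre-specify a directional within-person T1-to-T4 contrast with its interval, matching the secondary outcome. Use either an exact McNemar test or a time-only version of the logistic mixed model already named, fitted to all observed visits.
- Pre-specify a T2-to-T4 contrast so that postpartum relapse is visible.
- Describe the results as uncontrolled change, not as an effect of the intervention.

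The rule for missing visits can be left to the SAP. The change is analysis wording only, with no new data or visits. Intervals in 25 people, and more so within the two T1 groups, will be wide, and there will be no single omnibus p-value. The contrasts show direction but do not separate an intervention effect from spontaneous quitting; that would need a control group.

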Basic Study Information

1. * Title of study:

Partnering with Pregnant and Postpartum People to Co-Create a Novel Intervention to Reduce Tobacco and Cannabis Use

2. * Short title:

PICTURE Aim 3

3. * Brief description:

We will conduct a single group, proof-of-concept feasibility trial of a new intervention designed with guidance from the PICTURE community collaborative to address prenatal depressive symptoms to encourage tobacco and cannabis cessation.

4. * What kind of study is this?

Single-site study

5. * Will an external IRB act as the IRB of record for this study?

☐ Yes ☒ No

6. * Local principal investigator:

[name]

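### The efficacy analysis and the 70% power claim rest on an EUC control group that this single-arm trial of 25 participants does not have

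*Protocol*

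**What the plan says.** The design is stated consistently outside the statistics paragraph. Basic Study Information, item 3, says "We will conduct a single group, proof-of-concept feasibility trial of a new intervention", and item 4 gives "Single-site study". Study Design, item 2, says "This study is an experimental, single-arm feasibility trial", and item 1 enters 25 as total enrolment. Research Activities, item 1, describes one pathway: every participant has a baseline assessment, the prenatal sessions and three later assessments. There is no allocation step and no comparison condition.

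Study Design, item 8, is written for two groups. It plans:

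- chi-square tests of self-reported abstinence, INT against EUC, at Times 3 and 4;
- chi-square tests of biochemically verified abstinence and of depressive symptoms between the groups;
- two-sample t-tests on EPDS scores;
- a logit-link mixed model that "will be used to test the treatment effect (INT vs. EUC) and treatment by time interaction".

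It closes with this sample-size statement: "We have 70% power to detect a 15% difference in quit rates between INT and EUC, assuming a 25% intervention arm quit rate". For controls the same sentence assumes that 10% quit. EUC appears only in this paragraph and is not defined.

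**The concern.** A treatment effect and a treatment-by-time interaction cannot be estimated when every participant is treated, and a two-sample test needs a second sample. The only quantitative support offered for the sample size is a power figure for a comparison that the trial cannot make.

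The analyses affected are not peripheral. Study Aims item 1 and Study Design item 3 list abstinence from tobacco and cannabis as a primary outcome, and item 8 speaks of assessing preliminary efficacy. If the paragraph stands, the analysts will have to invent the abstinence analysis after seeing the data. Change over time in a single group also cannot be credited to the intervention. The inclusion criteria admit people who had already stopped using before enrolment, and the protocol's own background cites substantial postpartum relapse. Both would move abstinence rates with no intervention at all.

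**Working it through.** **Inputs from the protocol.** One arm; 25 participants; one site; quit rates of 25% (intervention) and 10% (control), a difference of 0.15; stated power 70%.

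**Inputs not stated, so assumed.** Alpha of 0.05 two-sided, with one-sided 0.05 and one-sided 0.10 as alternatives; 1:1 allocation; no dropout, which favours the stated power.

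**1. Sample size that would give the stated 70%.** Pooled two-proportion formula:

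n per arm = [z(alpha) × √(2p̄(1−p̄)) + z(power) × √(p1(1−p1) + p2(1−p2))]² / (p1−p2)²

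With p̄ = 0.175, √(2 × 0.175 × 0.825) = 0.5374. The second root is √(0.1875 + 0.09) = 0.5268. For 70% power, z = 0.524.

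- Two-sided 0.05: [(1.960 × 0.5374 + 0.524 × 0.5268) / 0.15]² = 78.6, so 79 per arm and 158 in total.
- One-sided 0.05: 59.8, so 60 per arm and 120 in total.
- One-sided 0.10: 41.4, so 42 per arm and 84 in total.

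Each total is more than three times the planned enrolment.

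**2. Power if 25 people were divided into two arms.** The protocol proposes no such split; this only shows scale.

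| Arms | Method | Power |
|---|---|---|
| 12.5 each | normal approximation, two-sided 0.05 | 16% |
| 12.5 each | normal approximation, one-sided 0.05 | 25% |
| 12.5 each | normal approximation, one-sided 0.10 | 38% |
| 13 and 12 | exact, uncorrected chi-square, two-sided 0.05 | 15% |
| 13 and 12 | exact, Fisher, two-sided 0.05 | 7% |

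**3. Power if 25 meant 25 per arm.** The normal approximation gives 28% (two-sided 0.05), 40% (one-sided 0.05) and 55% (one-sided 0.10). Exact power at two-sided 0.05 is 30% for chi-square and 18% for Fisher. The stated 70% is not reproduced.

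**4. One arm of 25 against a fixed 10%.**

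- Exact binomial, reject at 6 or more abstinent: one-sided alpha 0.033, power 62% at a true rate of 25%.
- Exact binomial, reject at 7 or more: one-sided alpha 0.009, power 44%.
- One-sample normal approximation, one-sided 0.05: (0.15 × √25 − 1.645 × √0.09) / √0.1875 = 0.59, power about 72%.

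The last figure is the closest to 70%, but it belongs to a test that the protocol does not describe.

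**5. What 25 participants can deliver.** Exact (Clopper-Pearson) 95% intervals: 6/25 abstinent (24%) gives 9% to 45%, and 18/25 (72%) gives 51% to 88%. With 20 completers, 14/20 (70%) gives 46% to 88%.

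**The case against.** The strongest reply is that this is a feasibility trial. Its stated hypotheses concern only feasibility and acceptability, and those measures need no control group. Some of item 8 also survives: the Cochran Q test is confined to the INT group, and the feasibility chi-square tests compare participant subgroups. That is right and limits the scope of the point. It does not rescue the INT versus EUC analyses, because abstinence is itself listed as a primary outcome.

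Second, alpha, sidedness, allocation and arm size are not given, so the 70% cannot be called an arithmetic error. It may have been correct for a two-arm design from which the text was carried over, although that origin is an inference. This stands as a limit on wording: the figure does not apply to this trial. The conclusion does not depend on the assumption, since even one-sided 0.10 would need 42 per arm.

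Third, the divided-sample power figures are counterfactual. They are, and the defect is structural without them.

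Leaving the matter to a statistical analysis plan is no answer. The protocol does not omit detail here; it commits to comparisons that its own design rules out.

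**Conclusion.** The point holds and must be fixed. Every INT versus EUC comparison in Study Design item 8 is undeliverable in the design described, and the 70% power statement is not a property of this trial. This follows from the protocol's own text and needs no assumption about alpha or allocation.

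The size of the mismatch does rest on assumptions (1:1 allocation, no dropout): 158 participants at two-sided 0.05, or 84 at one-sided 0.10, against 25 planned. The within-group Cochran Q test and the feasibility summaries are unaffected. No conclusion about efficacy, even a preliminary one, can be drawn from uncontrolled change in this group.

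**What to change.** Rewrite Study Design item 8 to match the single-arm design:

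- Remove the INT versus EUC chi-square tests and t-tests, their stratification by race and sexual orientation, the treatment and treatment-by-time terms in the mixed model, and the 70% power sentence.
- Report the proportion abstinent by self-report at each assessment with an exact 95% confidence interval. Show baseline abstinence alongside, since people who have already stopped may enrol. Report urine-verified abstinence at T4 only, the one time a sample is taken.
- Report within-person change in EPDS from T1 with a 95% confidence interval.
- The Cochran Q test may stay as a descriptive within-group analysis.
- Justify 25 by precision, using intervals such as those in step 5 of the working, and include the expected width after dropout.
- State that abstinence and EPDS results are descriptive and do not support an efficacy conclusion.

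If a comparison group is in fact intended, the alternative is to describe it throughout the protocol and recalculate the sample size, which would be a different trial.

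The cost of the single-arm route is one paragraph by IRB modification, with no added participants or procedures. The stated power is withdrawn.
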